Official title: Non-invasive Transcranial Direct Current Stimulation to Improve Cognitive Efficiency

NCT number: NCT05216315

Document date: July 28, 2023

Study Protocol

Eligibility Criteria:

Participants eligible for inclusion in the study must meet specific criteria based on their age, cognitive status, and health condition. For healthy older adults, the minimum age requirement is 65 years, and they must have a Montreal Cognitive Assessment (MCA) score greater than 26 points and a Geriatric Depression Scale (GDS) score between 1 and 3. Individuals classified as having Mild Cognitive Impairment (MCI) must also be at least 65 years old and have a MCA score between 21 and 26 points, with a GDS score falling between 1 and 3. Those categorized as having mild Alzheimer's disease (EA) must meet the same minimum age requirement of 65 years, with a MCA score ranging from 18 to 23 points and a GDS score between 3 and 4.

Exclusion Criteria:

Certain conditions disqualify individuals from participating in the study. These include contraindications to transcranial Direct Current Stimulation (tDCS), such as the presence of intracranial metal implants, intracranial hypertension, or a high risk of seizures. Additionally, significant asymptomatic neurovascular disease, a history of previous symptomatic stroke, alcohol or drug abuse/dependence, severe psychiatric symptoms, or depressive symptoms higher than mild are grounds for exclusion from the study.

Randomisation

Once patients were available, allocation to the anodal and sham tDCS groups was carried out by stratified block randomisation. Participants were randomly assigned using a random number system. They were randomly assigned to the experimental groups (anodal vs. sham) with a 1:1 ratio, with gender as the stratum. Participants did not know which group they had been placed in until the intervention ended, this being a single-blind study.

Procedure

Stimulation was performed using an HDC stimulator (Newronika TM, Milan, Italy), which is battery-driven and delivers a direct current. The current intensity was 2 mA, and the stimulation lasted 20 minutes. In addition, a current ramp was delivered for 30 seconds prior to the start and end of stimulation. A pair of 25 cm² rubber electrodes

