transferred the direct current. These electrodes were inserted into sponge pads soaked with sterile water. The electrodes and sponges were placed in a neoprene headcap with predefined and clearly annotated positions, based on a subset of the international 10-10 EEG system. The anode was placed on F3 at left dorsolateral prefrontal cortex (DLPFC), and the cathode was placed on the right frontal lobe (Fp2). Electrode placement and session duration were identical in active and placebo tDCS. However, in the placebo tDCS condition, at the end of the onset ramp, the current was automatically turned off for 20 minutes and then turned on again for the last 30 seconds.

In addition, to check the stimulations carried out, the HDCstim® stimulator is connected to the HDCprog, which has a “treatment report” in its menu. These reports show: a. Time and date of each stimulation, b. Average impedance of each stimulation (a suitable impedance range would be from 4 kOhm to 12 kOhm, and c. Result of the treatment (completed, failed or cancelled).

Additionally

Participants were fully informed about the study's blinding design and provided informed consent acknowledging their understanding and acceptance of the blinding procedure. Quality control measures were implemented to maintain consistency and accuracy in tDCS administration. Personnel received training in standardized electrode placement procedures and stimulation administration. Ongoing supervision ensured proper electrode placement and adherence to established protocols in all stimulation sessions, ensuring uniform treatment administration throughout the study.

Outcome

The primary outcome measures were general cognitive function, immediate and delayed memory, and learning ability. The secondary outcome measures included executive function tests. The selection of primary outcomes was based on the DSM-5 criterion (APA, 2013) that states that mild neurocognitive disorder due to possible Alzheimer's disease should show clear evidence of a decline in memory and learning. The assessment of memory and learning is a main criterion in the characterisation of the pathology, and we aimed to analyse the possible change in measures that analyse these variables. In addition, given that the progression of these patients to major neurocognitive disorder due to Alzheimer's disease is usually accompanied by a deterioration in executive control, change in the measures that assess this variable was proposed as a secondary outcome.

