Semantic fluency and phonological fluency subtests of the Barcelona Test Revised (TBR; Peña-Casanova 2005). The semantic fluency subtest requires the subject to evoke the maximum number of words linked to a specific category, "animals", in one minute. In the case of phonological verbal fluency, the subject is asked to recall the maximum number of words beginning with the letter "p" in a maximum of 3 minutes. This test evaluates the ability to access and recall elements from the lexical and semantic store. Among the processes involved, information processing speed, cognitive flexibility, and

working memory have been pointed out.

Statistical Analysis

A priori power calculation for ANOVA repeated-measures within-between interaction required a total sample of 32 participants to detect an effect size of .30 with 90% power, with alpha set at .05. Power calculations were carried out using GPower 3.1.7.

To analyse the sociodemographic variables, we used independent samples t-tests and chi-square tests. To analyse the cognitive variables, mixed ANOVAs with 2 groups (active vs. sham; between-subjects) X 2 sessions (before vs. after intervention; within-subjects) were conducted. The effectiveness of the tDCS should be reflected by finding a significant interaction between the two independent variables (in which the active group should improve across sessions, whereas the sham or control group would not). Post-hoc simple effects tests were conducted to analyse these significant interactions. A value of $p \leq .05$ was considered statistically significant. Data were analysed using SPSS 28.

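### The 2x2 mixed ANOVA silently becomes a completers-only analysis; the plan should name an analysis set and fit the same model to all randomised participants

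*Combined protocol and SAP*

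**What the plan says.** The Statistical Analysis section specifies one efficacy analysis for every cognitive outcome: "mixed ANOVAs with 2 groups (active vs. sham; between-subjects) X 2 sessions (before vs. after intervention; within-subjects) were conducted". A significant group-by-session interaction is to be read as evidence that stimulation works, with simple-effects tests to follow. The same section gives the sample size: the calculation "required a total sample of 32 participants to detect an effect size of .30 with 90% power, with alpha set at .05". SPSS 28 is the named software.

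Under Randomisation, participants are "randomly assigned to the experimental groups (anodal vs. sham) with a 1:1 ratio", stratified by gender. The Eligibility Criteria admit people aged 65 or over who are healthy, have mild cognitive impairment or have mild Alzheimer's disease.

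No section states who belongs to the analysis set, whether participants are analysed in the arm assigned, what happens when a post-test is missing, what dropout was expected, or how many people were randomised.

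**The concern.** A 2x2 repeated-measures ANOVA needs both scores from each person. Anyone without a post-test leaves the analysis, and the baseline score goes too. Outcomes are analysed one at a time, so different tests can rest on different subsets of the randomised sample.

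What remains is a comparison of change among completers, which randomisation no longer fully protects. On retest, low scorers tend to rise and high scorers to fall. If one arm loses more of its low scorers (or high scorers) than the other, the arms' completers start from different baselines, and regression to the mean enters the interaction as if it were a treatment effect. It can act in either direction. In an older sample that includes cognitively impaired people, a link between score and non-return is plausible.

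**Working it through.** **1. The interaction is a change-score test.** With two sessions, the interaction contrast is (post − pre in active) − (post − pre in sham), and its F(1, N−2) is the square of the two-sample t on change scores. No post-test means no change score.

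**2. The plan's own figure.** Inputs from the Statistical Analysis section: f = .30 (taken as Cohen's f, since the metric is not named), alpha .05, power 90%, 2 groups, 2 sessions. The pre-post correlation ρ is not stated. I assume .5, which reproduces the plan's total.

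- Noncentrality: λ = f² × N × m/(1 − ρ), with m = 2 and df = 1, N − 2.
- N = 32: λ = .09 × 32 × 2/.5 = 11.52; critical F(1, 30) = 4.17; power = 90.7%.
- N = 31 gives less than 90%, so 32 is the smallest total that reaches the target. The figure reproduces.
- Other correlations do not give 32: ρ = .3 needs 43 (44 for equal arms) and ρ = .7 needs 20.

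**3. Power by number of complete pairs** (ρ = .5, equal arms):

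| Pairs | λ | Power |
|---|---|---|
| 32 | 11.52 | 90.7% |
| 30 | 10.80 | 88.7% |
| 28 | 10.08 | 86.3% |
| 26 | 9.36 | 83.5% |

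**4. Bias when loss depends on baseline in one arm.** The documents give no dropout rate, so the losses here are assumptions: 16 per arm, standard normal scores, ρ = .5, and the k lowest baseline scorers in the active arm have no post-test. If completers' mean baseline shifts by s, their expected change shifts by −(1 − ρ) × s.

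- k = 3: the expected three lowest of 16 normal scores are −1.766, −1.285 and −0.990, which sum to −4.041. The 13 who remain average s = 4.041/13 = 0.311. Bias = −.5 × 0.311 = −0.16 SD.
- k = 4: the fourth is −0.763, so the sum is −4.804, s = 4.804/12 = 0.400 and bias = −0.20 SD.
- If the highest scorers are lost instead, the signs reverse: +0.16 and +0.20 SD.

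Simulation (20,000 runs per case) agrees. With no treatment effect, the ANOVA rejects in about 7.3% of trials for k = 3 and 8.3 to 8.6% for k = 4, against a nominal 5%. At the planned effect, losing the lowest scorers from active leaves power at about 77 to 79% (k = 3) and 72 to 74% (k = 4). Fewer pairs alone would leave 87.2% (16/13) and 85.6% (16/12).

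The planned effect is the square root of 11.52/8, or 1.2 SD of change. The SD of change is √(2 × (1 − .5)) = 1, so 0.16 SD is about 13% of it.

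**5. Milder cases, same set-up, three lost:**

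- at random from active: bias within about 0.01 SD, power 87 to 88%;
- lowest baseline scorers from both arms: bias within 0.01 SD, power 86 to 87%;
- from active with probability weight exp(−baseline): bias −0.09 SD, null rejection 5.7%;
- highest baseline scorers from active, with ρ = .8: (1 − .8) × 0.311 = +0.06 SD, null rejection 5.9%.

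**6. The mixed model under the same losses.** With only post-tests missing, the likelihood estimate of an arm's post-test mean is the completers' mean plus slope × (baseline mean of all randomised − baseline mean of completers). Its bias was within 0.01 SD in every case in step 4. If the three lowest *post-test* scorers in active are lost, however, the ANOVA is biased by about +0.16 SD and the mixed model by about +0.24 SD. With complete data the two give the same statistic (2.346 and 2.346 on one generated data set).

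**The case against.** The strongest reply is that no loss is reported or predicted, the text is in the past tense, and with complete data the ANOVA is exactly right. The sizes in step 4 also come from a harsh mechanism: strictly score-ordered loss, all from one arm. All of that stands. It limits the claim to a conditional risk and makes 0.16 to 0.20 SD a worst case for three or four losses, not an expected value.

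Four stronger readings are tempting, and the documents do not support them.

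- **That the first dropout takes the trial below its power target.** At 16/15, power is 89.7%, a shortfall of 0.3 points. Even that holds only if exactly 32 were randomised. The plan says only that the calculation "required a total sample of 32 participants to detect an effect size of .30 with 90% power" and never states the number enrolled.
- **That the device report shows outcome loss was foreseen.** The Procedure section lists "Result of the treatment (completed, failed or cancelled" as one field of that report. A failed or cancelled stimulation is not a missing post-test, and nothing excludes participants on that basis.
- **That the mixed model has no downside.** It relies on loss being explained by the observed baseline and arm. Step 6 shows it can do worse than the ANOVA when loss follows the unseen post-test score.
- **That the whole sample is cognitively impaired.** Healthy older adults are eligible too.

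What the reply does not answer is that the only efficacy analysis has no rule for anyone missing a post-test, and that a better method is available in the software already named.

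**Conclusion.** The point holds as a fixable weakness in the trial's one efficacy test. The planned interaction uses complete pairs only, and the plan gives no analysis set and no missing-data method. If loss depends on baseline differently by arm, the interaction is biased: up to about 0.16 to 0.20 SD in the worst case examined, and close to zero when loss is random or alike in both arms. These sizes assume a correlation of .5, 16 per arm and three or four losses, none of which the documents state.

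The power point is secondary. The figure of 32 is a number needed with both tests; 30 pairs give 88.7% and 28 give 86.3%, again at correlation .5.

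**What to change.** 1. Define the analysis set as every randomised participant, in the arm assigned.
2. Fit the same group-by-session model as a linear mixed model (SPSS MIXED: REML, unstructured 2x2 covariance, Satterthwaite degrees of freedom), keeping participants who have a baseline only.
3. Report, by arm and outcome, the numbers randomised and the numbers tested at both sessions.
4. Add a sensitivity analysis for loss that depends on the unseen post-test, for example by shifting the missing post-test scores by a range of amounts in each arm and showing where the conclusion changes.
5. State that 32 is the number with both tests, and give the power for the number who completed. If enrolment were still open, 32 pairs would need 36 randomised at an assumed 10% loss (32/.9 = 35.6) or 40 at 20% (32/.8).

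The cost is a few sentences in the plan, a different procedure in the same package and one extra analysis. The main analysis would then rest on missing-at-random, which is why step 4 belongs with it. If nobody was lost, the interaction test is unchanged.

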The Mini-Mental State Examination (MMSE; Folstein et al., 1975) was used as an index of global cognitive functioning; the maximum score is 30 points. This test was designed to estimate the existence and severity of cognitive impairment; it is a brief and quantitative test that measures general cognitive function.

Test de Aprendizaje Verbal Complutense (TAVEC; Benedet and Alejandre, 1998). This test presents a list of 16 words which, after being read by the evaluator, have to be repeated by the participant. The list is repeated five times (trials), and after 20 minutes, the participant is again asked to remember the 16 words. The test was administered to evaluate the participant's immediate memory (Trial 1), learning ability (analysing Trial 5 and the total number of correct answers on the five trials), and delayed memory.

Memory Alteration Test (M@T; Rami et al., 2007). The M@T provides efficient and valid screening for A-MCI and early-stage AD. The test evaluates different abilities such as: encoding, orientation, semantic memory, and free recall. The maximum score is 50 points.

Direct and inverse digits of the Wechsler Intelligence Scale for Adults-III (Wechsler, 2001). These tests assess attentional capacity by exposing the participant to increasing amounts of information. On the direct digits task, which is used to assess immediate recall, the subject must repeat the sequence of numbers in the same order in which they are read by the examiner. On the inverse digits task, which assesses working memory and mental flexibility, the subject must say the digits backwards from the way they were presented by the examiner. Both tests are evaluated in the same way, assigning one point for each correct item, with a maximum score of 16 for both tests.

Rey's Complex Figure (Rey, 1984). This test is used to evaluate both memory and executive capacity, such as planning, motor skills, working memory, and visuoconstructive and spatial ability. For its execution, the subject has to attentively reproduce a complex geometric drawing and later reproduce it after a three-minute delay.

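### The bracketed success pattern (active improves, sham does not) could, if applied as a condition, lead a true between-arm benefit to be reported as not effective

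*Combined protocol and SAP*

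**What the plan says.** In the Statistical Analysis section the cognitive variables are analysed by "mixed ANOVAs with 2 groups (active vs. sham; between-subjects) X 2 sessions (before vs. after intervention; within-subjects) were conducted". Effectiveness is then described: "The effectiveness of the tDCS should be reflected by finding a significant interaction between the two independent variables". A bracket follows that sentence and gives the shape of the interaction: "in which the active group should improve across sessions, whereas the sham or control group would not". The next sentence adds the follow-up: "Post-hoc simple effects tests were conducted to analyse these significant interactions".

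The same section gives the power calculation, which is for the within-between interaction. It "required a total sample of 32 participants" and was set "to detect an effect size of .30 with 90% power, with alpha set at .05".

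The Outcome section names general cognition, immediate and delayed memory, and learning as primary. They are measured by performance tests. For the word-list test, "The list is repeated five times (trials), and after 20 minutes, the participant is again asked to remember the 16 words". The document mentions no parallel forms, no interval between the two sessions and no allowance for practice. It also does not say that identical material was used twice.

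**The concern.** The bracket is the plan's only statement of direction. An F test of an interaction has none, so a reader who wants to know which significant interactions count as benefit will turn to the bracket, and from there to the simple-effects tests.

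The pattern is narrower than the between-arm question. On memory and learning tests taken twice, sham may improve because participants have done the task before, and a randomised sham arm is there to subtract that gain. Sham improvement is then no evidence against stimulation. In the other direction, the Outcome section itself describes decline in these patients. Active holding steady while sham falls would be a benefit, yet active would not have improved.

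What is at stake is the stated conclusion. If the bracket is a condition, a true difference in change can be reported as not meeting the definition of effectiveness. If it is only an expectation, the plan does not say what is concluded when the interaction is significant and sham also improves, so that choice can be made after the data are seen.

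**Working it through.** **Inputs.** From Statistical Analysis: effect size .30 (read as Cohen's f), N = 32, power 90%, alpha .05, two groups, two sessions. From Randomisation: 1:1 allocation, hence 16 per arm. Assumed: pre-post correlation r = .5 (not stated) and sphericity, which is automatic with two sessions.

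**Step 1: reproduce the plan's N.** For the within-between interaction with m = 2 sessions,

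λ = f² × N × m / (1 − r) = 0.09 × 32 × 2 / 0.5 = 11.52, with 1 and N − 2 = 30 df.

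The noncentral F gives power of 90.7%. N = 30 gives 88.7%, so 32 is the smallest even N that reaches 90%. The plan's figure reproduces. With r = .3 the power at N = 32 would be 79%, and with r = .7 it would be 99%; r = .5 is the value that matches the stated 32.

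**Step 2: put the effect on the change-score scale.** In a 2 × 2 design the difference in change is 4f = 4 × 0.30 = 1.2 SD of a single score. The SD of change is √(2(1 − r)) = √(2 × 0.5) = 1 in the same units, so the difference is 1.2 SD of change. Check: λ = (16/2) × 1.2² = 8 × 1.44 = 11.52.

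**Step 3: compare two rules.** Let g be the mean change in sham, and g + 1.2 the mean change in active. Rule A is a significant interaction favouring active. Rule B applies the bracket literally: rule A, and active significantly better, and sham not significantly better, using simple effects with pooled error and 30 df. Because g cancels from the between-arm difference, rule A cannot depend on it. Simulation with 400,000 trials of 16 per arm gives:

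| Sham change g (SD) | Active change (SD) | Rule A | Rule B |
|---|---|---|---|
| −1.2 | 0 | 91% | 3% |
| −0.5 | +0.7 | 91% | 75% |
| 0 | +1.2 | 91% | 90% |
| +0.25 | +1.45 | 91% | 80% |
| +0.5 | +1.7 | 91% | 50% |
| +0.75 | +1.95 | 91% | 17% |

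The −1.2 row is the case of active steady and sham falling: active has zero mean change, so its simple effect is significant in the right direction in only about 2.5% of trials. In the −0.5 row active still improves by 0.7 SD, so that row does not represent this case.

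Separate paired t-tests in place of pooled error change little: 52% instead of 50% at +0.5 SD.

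**Step 4: false positives.** With no treatment effect, the two-sided interaction test rejects in about 5% of trials at every drift examined. Rule B is met in at most 2.4%. The problem is lost true benefits; there is no inflation of type I error.

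**The case against.** The strongest reply is that the bracket is not a decision rule. The operative words make the significant interaction the evidence of effectiveness, and the interaction is the only test that is powered. No sentence says that a sham gain overturns it. The simple-effects tests are called post hoc, follow a significant interaction, and are not said to be within-arm: in a 2 × 2 design they could equally compare the groups at each session. Rule B above is therefore a literal construction of the bracket, and the plan does not write it out. All of this stands.

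A reader might infer that practice gain will make a working treatment fail the trial's own criterion. The documents do not support that. It could happen only if the bracket is enforced as a condition, and the loss is limited at small gains (90% to 80% at 0.25 SD). A reader might also infer that the same word list and figure were used twice, so that sham improvement is to be expected. The text is silent on forms and retest interval and gives no practice size; the 50% and 17% figures need gains of 0.5 and 0.75 SD that nothing in the documents establishes. Nor does the document give a duration that would make a 1.2 SD decline likely, and the eligibility criteria also admit healthy older adults.

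What the reply does not remove is the gap. Read literally, the bracket leaves no room for sham to improve, and read loosely, it leaves the conclusion undefined when sham does.

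**Conclusion.** The point holds as a defect of the wording that defines effectiveness. It is not a defect of the primary test. The interaction is a valid between-arm comparison, with about 91% power at the planned effect whatever drift the arms share. The attached pattern, if applied as a condition, would be met in about 90%, 80%, 50% and 17% of trials at common gains of 0, 0.25, 0.5 and 0.75 SD, and in about 3% if active holds steady while sham falls 1.2 SD.

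These figures rest on r = .5, on drift that adds equally to both arms, on normally distributed change, and on drift sizes chosen for illustration. Severity is moderate: the rule for the conclusion needs changing, while the data, sample size and primary test do not.

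**What to change.** Replace the bracketed clause so that the sentence reads:

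> Effectiveness is shown by a significant group × session interaction in which change from before to after is more favourable with active than with sham, reported as the between-arm difference in change with its 95% CI; simple-effects tests are descriptive and are not part of the success criterion.

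This keeps the direction that the F test lacks and settles the case in which both arms improve or both decline. It would also help to state which test forms were used at each session and the interval between sessions, so that readers can judge how much retest gain to expect.

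The cost is one sentence of wording, with no new data and no change to N or to the mixed ANOVA.
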